7.1.4.1 Adverse Events of Special Interest

Not applicable.

7.1.5 Methods for Recording Adverse Events and Serious Adverse Events

Findings regarding Adverse Events must be reported on an Adverse Events eCRF, as specified in section 7.1.1, Solicited Adverse Events, and on the VSAE form, if applicable, which is part of the Investigator Site File. All findings in subjects experiencing AEs must be reported also in the subject's source document.

All SAEs which occur during the course of the study, whether considered to be associated with the study vaccination or not, must be reported within 24 hours of the site becoming aware of the event to GSK or its designee. Specific instructions and contact details for collecting and reporting SAEs to GSK will be provided to the investigator.

All SAEs are also to be documented on the Adverse Events eCRF. Any medication or other therapeutic measures used to treat the AE will be recorded on the appropriate eCRF(s) in addition to the outcome of the AE.

After receipt of the initial report, representatives of GSK or its designee will contact the investigator if it is necessary to obtain further information for assessment of the event.

All SAEs must be reported by the investigator to his/her corresponding EC OR IRB OR applicable regulatory authorities] in accordance with institutional policy/regulatory requirements and adequate documentation of this notification must be provided to the Sponsor.

GSK or its designee must also comply with the applicable regulatory requirement(s) related to the reporting of suspected unexpected serious adverse vaccine reactions (also known as SUSARs) to the regulatory authority(ies) and the IRB/EC. If a SUSAR or other safety signal relating to use of one of the study vaccines is reported to GSK or its designee, the Sponsor will communicate the information to the investigator and the investigator will be responsible for submitting this information to the EC,, IRB and other relevant authorities.

7.1.5.1 Post-Study Events

Any SAE that occurs outside of the protocol-specified follow-up period and considered to be caused by the study vaccine must be reported to GSK or its designee. These SAEs will be processed by GSK or its designee as during the course of the study, until 6 months after end of the study. Instructions and contact details for collecting and reporting these suspected SAEs will be provided to the investigator.

7.1.6 Pregnancies

To ensure subjects' safety, each pregnancy in a subject after study vaccination must be reported to GSK or delegate within 72 hours of the site learning of its occurrence. If the subject agrees to submit this information, the pregnancy must be followed to determine outcome, including spontaneous or voluntary termination, details of the birth, and the presence or absence of any birth defects, congenital abnormalities, or maternal and/or newborn complications. This follow-up should occur even if intended duration of safety follow-up for the study has ended.

Pregnancy data must be recorded on a Pregnancy Report eCRF (initial report) and Pregnancy Follow-Up eCRF (outcome report) and reported to GSK or delegate. Instructions and contact details for submitting the Pregnancy eCRFs will be provided to the investigator.

Any pregnancy outcome meeting the definition of a SAE (see section 7.1.4, Serious Adverse Events) must also be reported on the VSAE Report Form.

7.1.7 Safety Laboratory Measurements

This study has no safety laboratory measurements.

7.2 Efficacy Assessment

This study has no efficacy assessments.

7.3 Immunogenicity Assessment

The measures of immunogenicity used in this study are standard, i.e., widely used and generally recognized as reliable, accurate, and relevant (able to describe the quality and extent of the immune response). Testing will be conducted by a GSK or designated laboratory in a blinded manner towards the treatment arm and the visit.

The functional measure of immunogenicity used in this study, Serum Bactericidal Assay (SBA), is a measure of the ability of antibodies, mediated with complement, to kill meningococci, and is widely used and generally recognized as the serological correlate of protection. Human Serum Bactericidal Assay using human complement (hSBA) for *N.meningitidis* serogroups A, C, W, Y and serogroup B strains will be performed in GSK, Clinical Laboratory Sciences, Marburg (Germany) or in a qualified and certified laboratory designated by GSK using the identical standardized, validated procedures with adequate controls.

(Amended 4 April 2018)

7.3.1 HT-hSBA

The High Throughput human Serum Bactericidal Assay using human plasma as the source of exogenous complement (HT-hSBA) will be used to measure the induction of functional complement dependent bactericidal antibodies directed against meningococcal serogroups A, C, W and Y and serogroup B strains following the study vaccination. The key measures of immunogenicity will be the percentages of subjects with hSBA ≥ LLOQ, hSBA GMTs, and the percentage of subjects with four-fold titer rise against serogroups A, C, W and Y and serogroup B strains. A post-vaccination hSBA titer ≥4 is used as an accepted correlate of protection against invasive meningococcal disease (Goldschneider et al, 1969a; Goldschneider, et al 1969b). *The sample testing schedule is summarized in Table 7.3-1*.

Table 7.3-1: Sample Testing Schedule in V102_15E1

Aggar Tyma	Subject meet	V102_15E1 (extension study)				
Assay Type	Subject pool	Day 1	Day 6	Day 31	Day 66	Day 91
HT-hSBA	Follow-on	$\sqrt{}$	√	$\sqrt{}$		
(all enrolled)	naive	V		V	V	V

HT-hSBA = high throughput human serum bactericidal assay

Serum bactericidal activity against *N. meningitidis* serogroup B strains will be determined by performing HT hSBA against four meningococcal B test strains M14459 (fHBP), 96217 (NadA), NZ98/254 (PorA) and M07-0241084 9 (NHBA). Each of these strains measures bactericidal activity primarily directed against one of the major bactericidal antigens included in the vaccine: strain M14459 measures hSBA against the fHBP variant 1.1; strain 96217 measures hSBA against antigen NadA; strain M07-0241084 measures hSBA against antigen NHBA and strain NZ98/254 measures hSBA against PorA P1.4, the immunodominant antigen in the OMV NZ vaccine component.

In case of insufficient blood volume to perform assays for all antigens, the sample will be analyzed according to priority ranking provided in Table 7.3-2.

Table 7.3-2: Immunological readouts and priority testing

Sample time points	Groups	No. of Subjects	Assay (strain/serogroup)	Priority rank
Follow-on subjects: Day 1, Day 6, Day 31 Naive subjects: Day 1, Day 31, Day 66, Day 91	All groups: B_0_2, ABCWY_0_2,ABCWY_0_6, ABCWY_0_2_6 Naive_ABCWY Naive_B	Up to 652 Follow-on subjects 200 Naive subejets	fHBP	1
			NHBA	2
			NadA	3
			PorA	4
			Serogroup C	5
			Serogroup Y	6
			Serogroup W	7
			Serogroup A	8

Collected samples may be used in other assays, for test improvement or development of analytical methods related to the study vaccines or the disease under evaluation to allow a more reliable measurement of the vaccine response. Under these circumstances, additional testing on the samples may be performed by GSK outside the scope of the protocol. Any sample testing will be done in line with the consent of the subject or/and subject's parent/ guardian.

8. STATISTICAL CONSIDERATIONS

8.1 Endpoints

8.1.1 Primary Endpoint(s)

8.1.1.1 Primary Effectiveness Endpoint(s)

This study does not have primary effectiveness endpoints.

(Amended 4 April 2018)

8.1.1.2 Primary Immunogenicity Endpoint(s)

The following will be summarized at 24 months after the last meningococcal vaccination for all follow-on subjects and at Day 1 in the extension study for naïve subjects:

- Percentages of subjects with HT-hSBA titers ≥LLOQ against each of four serogroup B test strains, and against N. meningitidis serogroups A, C, W and Y (only for MenABCWY groups).
- HT-hSBA GMTs against each of four serogroup B test strains, and against N. meningitidis serogroups A, C, W and Y (only for MenABCWY groups).

(Amended 4 April 2018)

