Blood sample: Collected prior to vaccination. 3 samples for follow-on subjects—20 mL at Day 1, Day 6 and Day 31. For naive subjects 4 samples of 20 ml each will be collected—at Day 1, Day 31, Day 66 and Day 91.

Data collection: eDiary for local and systemic reactions; Electronic Case Reporting Form (eCRF)

Clinic visits: At **D**ay 1, subjects will be assessed for eligibility and then enrolled into the study. After signing informed consent (and/or assent, as applicable), subjects will undergo a review of medical history and prior medications/vaccinations (since end of study V102_15 for follow-on subjects and since birth for naive subjects), and a physical assessment. All newly recruited subjects will be in the naive group and these will be randomized 1:1 to receive MenABCWY or rMenB+OMV using IRT. No randomization to treatment arm for follow-on subjects is required as vaccine groups remain the same as in the parent study V102_15; however, allocation of treatment will be done using IRT. A blood sample of ~20 mL will be collected at Day 1 from all subjects.

Follow-on subjects will also have a clinic visit at Day 6 for a blood draw of 20 mL. At **D**ay 31, all subjects will have a 20 mL blood draw and a safety evaluation. Naive subjects will receive their second dose of MenABCWY or rMenB+OMV at **D**ay 61 to complete the series, and have 2 subsequent blood draws at **D**ays 66 and 91. **See Table 4 for testing schedules.**

Table 4: Sample Testing Schedule in V102 15E1

Assay Type	Cubiaat naal	V102_15E1 (extension study)									
	Subject pool	Day 1	Day 6	Day 31	Day 66	Day 91					
HT-hSBA (all enrolled)	Follow-on	1/	1/	√							
	Naive	√		1	√	1/					

HT-hSBA = high-throughput human serum bactericidal assay

All subjects will be followed for 6 months after last vaccination for safety and then terminated from the study in a safety phone call.

Vaccination: At Day1, follow-on subjects from the ABCWY_0_2, ABCWY_0_6, and ABCWY_0_2_6 groups will receive 1 booster dose of MenABCWY. Subjects from the B_0_2 group will receive a booster dose of rMenB+OMV. Naive subjects will be randomized 1:1 to receive either 2 doses of MenABCWY or 2 doses of rMenB+OMV at Day 1 and at Day 61.

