2. OBJECTIVES

2.1 Primary *Immunogenicity* Objective(s)

1. To assess the persistence of bactericidal antibodies in subjects who previously received 2 or 3 doses of MenABCWY (administered according to 0, 2-, 0, 6- and 0, 2, 6-month schedules) or 2 doses of rMenB+OMV (given at a 0, 2-month schedule), 24 months after the last meningococcal vaccination in study V102_15 compared with baseline antibody levels in meningococcal naive subjects at enrolment, as measured by percentages of subjects with HT-hSBA titers ≥ LLOQ and HT-hSBA GMTs against N. meningitidis test strains for serogroup B¹ and serogroups A, C, W, and Y.

(Amended 4 April 2018)

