3. STUDY DESIGN

3.1 Overview of Study Design

Experimental design: Phase 2b, multi-center study in healthy adolescents 12-20 years with six study groups: four follow-on groups and 2 naïve groups.

Eligible follow-on subjects from the parent trial are those in groups ABCWY 0 2, ABCWY 0 6, ABCWY 0 2 6 and B 0 2, who have indicated willingness to participate in the extension at the time of termination from parent study, have received all planned meningococcal vaccinations in V102 15 (irrespective of administration within protocolspecified window), and have not received any additional meningococcal vaccinations since the last meningococcal vaccination in the V102 15 study. Up to 652 subjects who participated in the parent study V102 15 from Finland and Poland are eligible to be invited for enrolment in this extension study at approximately 24 months (-1/+3 months) after last meningococcal vaccination in the parent study. These subjects will be contacted by phone to check whether they are still interested in participating in the extension study, approximately 0-3 months prior to planned visit 1. All eligible subjects from Finland and Poland who are willing to participate in the extension study will be enrolled. Subjects will be analyzed in the vaccine groups that they were allocated to in the parent study. In addition, a newly enrolled Naive group will consist of 200 meningococcal vaccine-naive subjects of similar age, approximately 12 to 20 years old, to serve as a control for evaluating antibody persistence. Naive subjects are planned to be enrolled across all participating sites, based on the individual site's capacity to enroll. The number of Naive subjects enrolled per country will be proportional to the number of follow-on subjects enrolled from that country.

As a multicenter study, to ensure consistency of data, the participating staff will be trained in a uniform fashion and sites will be monitored to ensure consistency in study execution across all centers.

Duration of the study: The study duration is approximately 180 days for follow on subjects and 240 days for the naive subjects.

Study groups:

- ABCWY_0_2: subjects who received 2 doses of MenABCWY vaccine at Visit Month 0 and Visit Month 2 in study V102_15, and will receive 1 dose of MenABCWY in the extension study;

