- ABCWY_0_2_6: subjects who received 3 doses of MenABCWY vaccine at Visit Month 0, Visit Month 2 and Visit Month 6 in study V102_15, and will receive 1 dose of MenABCWY in the extension study;

- B_0_2: subjects who received 2 doses of rMenB+OMV vaccine at Visit Month 0 and Visit Month 2 in study V102_15, and will receive 1 dose of rMenB+OMV in the extension study;
- ABCWY_0_6: subjects who received 2 doses of MenABCWY vaccine at Visit Month 0 and Visit Month 6 in study V102_15, and will receive 1 dose of MenABCWY in the extension study;
- Naive: approximately 200 subjects who are meningococcal vaccine-naive and of similar age to subjects enrolled from the parent study, and will receive either 2 doses of MenABCWY or rMenB+OMV in the extension study.

Table 3.1-1: Study Groups/planned sample size in V102 15E1

	02_15 ry Study)	V102_15E1 ~24 months after last meningococcal vaccination in parent study			
Group	Vaccine (schedule)	Group	Number of Subjects*		
ABCWY_0_2	MenABCWY (0, 2 months)	ABCWY_0_2	up to 196		
ABCWY_0_2_6	MenABCWY (0, 2, 6 months)	ABCWY_0_2_6	up to 130		
B_0_2	rMenB+OMV (0, 2 months)	B_0_2	up to 196		
ABCWY_0_6	MenABCWY (0, 6 months)	ABCWY_0_6	up to 130		
		Naive (freshly enrolled)	200		

^{*}Maximum enrolment derived from planned enrolment per group in parent trial

(Amended 4 April 2018)

Table 3.1-2: V102_15E1 Blood Draw and Vaccination Schedule for follow-on subjects

	Target		Day 1	Day 6	Day 16		Day 31	Day 91	Day 181
Group	enrolment	Blood Draw	Vaccination	Blood Draw		Blood Draw		Phone Call for Safety Assessment	
ABCWY_0_2	100	20 mL	MenABCWY	20 mL	Safety	20 mL			Phone Call for Safety
B_0_2	100	20 mL	rMenB+OMV	20 mL	Phone call	20 mL	Safety Evaluation		Assessment and Study
ABCWY_0_2_6	100	20 mL	MenABCWY	20 mL		20 mL			Termination
ABCWY_0_6	100	20 mL	MenABCWY	20 mL		20 mL			

Table 3.1-3: V102_15E1 Blood Draw and Vaccination Schedule for Naive subjects

			Day 1	Day 16	Day 31	Day 61	Day 66	Day 76	D	ay 91	Day 151	Day 241
	N	Bloo d Dra w	Vaccinatio n	Safet	Bloo d Dra w	Vaccinatio n	Bloo d Dra w	Safet	Bloo d Dra w	Safety	Phone Call for Safety Assessme	Phone Call for Safety Assessme
Naive_ABCW Y	10 0	20 mL	MenABCW Y	Phon e call	20 mL	MenABCW Y	20 mL	Phon e call	20 mL	Evaluatio n	nt	nt and Study
Naive_B	10 0	20 mL	rMenB+OM V		20 mL	rMenB+OM V	20 mL		20 mL			Terminati on

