4. SELECTION OF STUDY POPULATION

4.1 Inclusion Criteria

Follow-on Participants

- Subjects from Finland and Poland previously enrolled in study V102_15 who have received all planned meningococcal vaccinations in the study¹
- Who have not received any additional meningococcal vaccination since the last meningococcal vaccination administered in the parent trial.
- Who have given written informed consent or assent (as applicable) after the nature of the study has been explained according to local regulatory requirements, prior to study entry. If the subject is under age 18 at the time of enrollment, the parent(s)/ legal guardian(s) of the subject should have given their written consent.
- Individuals of who the investigator believes can and will comply with the requirements of the protocol (e.g. use of an eDiary, return for follow-up visits, available for phone contacts).
- Individuals in good health as determined by the outcome of medical history, physical examination and clinical judgment of the investigator.

Naive Group

• Male and female individuals of similar age (approximately 12-20 years) to follow-on subjects from V102_15 trial.

- Who have not received any meningococcal vaccination since birth
- Individuals who have given their written informed consent or assent (as applicable) after the nature of the study has been explained according to local regulatory requirements, prior to study entry. If the subject is under age 18 at the time of enrollment, the parent(s)/ legal guardian(s) of the subject should have given their written consent.
- Individuals of who the investigator believes can and will comply with the requirements of the protocol (e.g. use of an eDiary, return for follow-up visits, available for phone contacts).

_

¹ Subjects will be eligible if they have received meningococcal vaccinations according to randomization assignment, irrespective of protocol-specified window.

• Individuals in good health as determined by the outcome of medical history, physical examination and clinical judgment of the investigator.

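### The Day 1 A, C, W, Y endpoint wording leaves out B_0_2 (and, read literally, Naive_B) although other sections call for all groups, and no supportive contrast with B_0_2 is planned

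*Protocol*

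**What the plan says.** **The restriction.** Protocol 8.1.1.2 defines primary Day 1 endpoints "against N. meningitidis serogroups A, C, W and Y (only for MenABCWY groups". The synopsis has the same limit for the percentages and the GMTs.

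**The testing plan.** Protocol Table 7.3-2 lists "All groups: B_0_2, ABCWY_0_2,ABCWY_0_6, ABCWY_0_2_6", together with Naive_ABCWY and Naive_B, for all eight assays, with C, Y, W and A at priority ranks 5 to 8. The testing schedules in Tables 4 and 7.3-1 are labelled "HT-hSBA (all enrolled").

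**The groups.** Protocol 3.1 describes B_0_2 as "subjects who received 2 doses of rMenB+OMV vaccine at Visit Month 0 and Visit Month 2 in study V102_15", and the listed rMenB+OMV composition contains no A, C, W or Y conjugate. The footnote to Protocol 4.1 ties follow-on eligibility to the parent assignment: "Subjects will be eligible if they have received meningococcal vaccinations according to randomization assignment, irrespective of protocol-specified window". The comparators are different people: "a newly enrolled Naive group will consist of 200 meningococcal vaccine-naive subjects of similar age". They are randomised only between the two vaccines.

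**The named comparator.** Protocol 2.1 assesses persistence for serogroup B strains and for A, C, W and Y "compared with baseline antibody levels in meningococcal naive subjects at enrolment". SAP 2 and 11.2 repeat that objective.

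**The concern.** There are two linked problems.

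First, the endpoint definition and the rest of the plan disagree on which groups have Day 1 A, C, W, Y results. A programmer following 8.1.1.2 literally would leave out B_0_2. The same programmer would also leave out Naive_B, whose members are as unvaccinated at Day 1 as those of Naive_ABCWY.

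Second, the only planned contrast between people who did and did not receive A, C, W, Y antigens is with new recruits. Their entry rules differ from those of the follow-on groups: no meningococcal vaccine since birth rather than since the last parent dose, meningococcal disease excluded at any time rather than since parent termination, and a differently defined immunosuppressant exclusion (Protocol 4.1 and 4.2). Age is required only to be similar, within about 12 to 20 years. SAP 8.1 leaves percentages unadjusted and puts only vaccine group and center in the ANOVA. The planned subgroups are country, gender and race (Protocol 8.3.7, SAP 8.6), so age is not examined there either. A difference in background seropositivity between new recruits and parent-trial subjects would pass straight into the persistence estimate. B_0_2 shares the parent trial and the follow-on entry criteria with the MenABCWY arms, and its sera are already scheduled for the assays.

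**Working it through.** **1. The plan's own figure.** The group maxima in Protocol Table 3.1-1 give 196 + 130 + 196 + 130 = 652 follow-on subjects, and 652 + 200 = 852. Both match the synopsis. There is no power figure to reproduce: Protocol 8.5 reads not applicable, and 8.4.2.2.1 states no hypotheses.

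**2. Which groups have Day 1 A, C, W, Y results?**

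| Place | Groups |
|---|---|
| Protocol 8.1.1.2; synopsis endpoints | MenABCWY groups only |
| Synopsis, statistical analyses | Every vaccine group |
| Protocol 8.4.2.2.3 (GMTs) | Every study group |
| FAS Persistence (Protocol 8.3.4, SAP 7.3) | No MenABCWY limit at Day 1, although the post-vaccination sets have one |
| SAP 11.2 | Restates the objective; silent on the limit |
| SAP 11.3, methods for A, C, W, Y (Day 1 included) | Every treatment group |

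None of these places names a MenABCWY versus B_0_2 contrast for A, C, W, Y.

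**3. Precision.** The documents give no seropositivity rates, so these are assumed: 50% or 70% at or above LLOQ after MenABCWY, and 10%, 20% or 40% background. The Miettinen-Nurminen 95% limits are the values d that solve (p1 − p2 − d)/√v(d) = ±1.96. Here v(d) = [r1(1 − r1)/n1 + r2(1 − r2)/n2]·N/(N − 1), N = n1 + n2, and r1, r2 are the maximum-likelihood rates restricted to r1 − r2 = d.

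| Comparator | Half-width at 50% vs 20%, arm of 100 | Same, arm of 130 | Range over all assumed rates, arm of 100 to 130 |
|---|---|---|---|
| 200 naive, pooled | 11.2 | 10.2 | 8.9 to 11.8 |
| 100 naive (Naive_ABCWY only) | 12.5 | 11.6 | 9.9 to 13.6 |
| B_0_2 at its maximum, 196 | 11.2 | 10.2 | 8.9 to 11.9 |
| B_0_2 at its target, 100 | 12.5 | 11.6 | 9.9 to 13.6 |

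ABCWY_0_2 may also reach 196. By the simple formula 1.96·√(p1q1/n1 + p2q2/n2), 196 versus 196 at 50% and 20% gives 1.96·√(0.25/196 + 0.16/196) = 9.0 points.

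With a 5% loss of results, a rate found only in the superseded text of the amendment log, the same formula gives 11.6 points for 95 versus 190, 12.9 for 95 versus 95, and 10.5 for 123 versus 186.

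**4. Possible shift in the naive contrast.** A background gap of X points moves the naive contrast by X points. For illustration only, a rise of 2 to 3 points per year of age with a gap of 1 to 2 years gives 2×1 to 3×2, or 2 to 6 points. Neither input is in the documents.

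**5. What B_0_2 can show about the naive background.** At equal true rates of 10%, 20% and 40%, the 95% interval for B_0_2 (n = 196) minus 200 naive is ±6.1, ±7.9 and ±9.6 points. With B_0_2 at 100 it is −6.8 to +8.2, −9.1 to +10.2 and −11.5 to +11.9. A gap of 2 to 6 points would generally lie inside these limits, so this is a coarse check.

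**6. Timing.** Day 1 falls about 24 months after the last parent dose. That dose is at Month 2 for B_0_2 and ABCWY_0_2, and at Month 6 for ABCWY_0_6 and ABCWY_0_2_6. B_0_2 is therefore sampled about 6 − 2 = 4 months earlier after parent entry than the two Month 6 arms. On the illustrative slope this is 4/12 × 2 to 3, or about 0.7 to 1 point. ABCWY_0_2 versus B_0_2 has no planned timing gap.

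**The case against.** The strongest reply is that naive subjects were always the intended control. The objective names them for every group and antigen, and B_0_2 was never a planned A, C, W, Y comparator. The study is descriptive, with no success criteria. Naive recruits are to be of similar age, enrolled across participating sites, with country numbers proportional to follow-on enrolment, and the GMT model includes center. All of this stands. It means that the B_0_2 contrast is a supportive addition and not the repair of a broken primary analysis.

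The randomised basis of such a contrast is also weakened. Follow-on subjects must be willing, have had all planned doses and have had no later meningococcal vaccine. All three conditions arise after randomisation and could differ by arm. B_0_2 subjects also received OMV and protein antigens, which might induce cross-reactive killing. A reader might infer that the contrast would let the trial attribute a Day 1 difference to vaccination as a randomised comparison does. The documents do not support that.

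A reader might also infer that the plan discards B_0_2's A, C, W, Y results, or that the restriction is why the comparison rests on naive recruits. Neither follows. The methods text, the Day 1 full analysis set and SAP 11.3 retain all groups, and the objective chose the naive comparator independently of the endpoint bullets.

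**Conclusion.** The point holds as an inconsistency with a modest missed opportunity. The endpoint bullets limit Day 1 A, C, W, Y to MenABCWY groups, while the testing table, the methods text, the Day 1 full analysis set and SAP 11.3 do not. Taken literally, the limit halves the naive comparator from 200 to 100. At an assumed 50% versus 20%, that widens the half-width by about 1.3 to 1.4 points (11.2 to 12.5, or 10.2 to 11.6).

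What a B_0_2 contrast adds is a comparator of the same origin as the MenABCWY arms, and not precision. At 196 it matches the naive group almost exactly. At 100 its half-width is about 1 to 2 points wider. These figures rest on the assumed rates.

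The documents do not show that the naive contrast is biased; the 2 to 6 points are an illustration. Comparisons between MenABCWY schedules, including 2 versus 3 doses, are unaffected, because those arms come from the parent randomisation.

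**What to change.** - Reconcile Protocol 8.1.1.2, the synopsis endpoints and SAP 11.2 so that Day 1 A, C, W, Y results are reported for all six groups.
- Pool Naive_ABCWY and Naive_B at Day 1, since neither has yet been vaccinated, and keep naive subjects as the named comparator.
- Add ABCWY_0_2, ABCWY_0_6 and ABCWY_0_2_6 minus B_0_2 at Day 1 for A, C, W and Y, with Miettinen-Nurminen intervals for differences and GMT ratios from the same ANOVA. Label them supportive.
- State the limits beside the table: selection into the extension after randomisation, possible cross-reactive killing from rMenB+OMV, and the roughly 4-month sampling difference from the Month 6 arms. Name ABCWY_0_2 versus B_0_2 as the cleanest contrast.

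The cost is an edit to the endpoint and SAP wording and one supportive table. No extra sera, visits or assays are needed beyond those scheduled, and no error rate is affected because nothing is tested. The main risk is over-reading the new contrast as fully randomised, which the stated limits address.
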